9.4. Safety Analyses

The safety analyses will be based on the Safety population. Safety will be assessed by summarizing and analyzing adverse events, laboratory analytes, vital signs, ECG parameters, and concomitant medications.

The severity of all adverse events is to be evaluated by the investigator based on the National Cancer Institute's CTCAE. All adverse events will be coded to preferred term and system organ class using MedDRA 19.1 or higher. The incidence of adverse events will be presented by MedDRA system organ class and preferred term, relationship to study drug treatment, and severity. A patient reporting the same adverse event more than once is counted once, and at the maximum severity or strongest relationship to study drug treatment when calculating incidence.

Laboratory data consist of chemistry, hematology, and hormonal tests. Only data collected by the central laboratory will be used for analyses. The National Cancer Institute CTCAE will be used to categorize toxicity grade for the laboratory parameters. Shift tables will be provided for each gradable parameter to summarize baseline toxicity grade versus post-baseline toxicity grade. For laboratory parameters that are not gradable by the CTCAE, a shift table based upon the normal range (low, normal, and high) will be provided for each parameter to summarize the baseline versus post-baseline results.

9.5. Pharmacokinetic Analyses

Plasma relugolix concentrations will be listed and summarized and included in the clinical study report.

PK data may be pooled with data from other studies in healthy male patients and patients with prostate cancer for population PK analysis, including evaluation of covariates of relugolix PK parameters, and for input into a population PK/pharmacodynamics models describing the relationship between relugolix exposure and serum testosterone [Ahsman, 2016]. These population PK analyses will be detailed further in a separate statistical analysis plan and report.

For patients from China and Japan in the PK subset, plasma relugolix PK parameters C_{max} , $AUC_{0-\tau}$, and t_{max} from Day 1 and Day 14 of dosing will be determined. Population PK or

PK/pharmacodynamic analyses may be conducted to explore the factors that affect relugolix exposure or to contribute to the assessment of the relationships between exposure and testosterone.

9.6. Endocrine Marker Analyses

Endocrine markers will be analyzed to see effects of relugolix and leuprolide acetate as measured as absolute value and change from baseline for:

- LH at Day 4, Week 5, Week 25, and Week 49 visits and/or follow-up visit(s);
- FSH at Day 4, Week 5, Week 25, and Week 49 visits and/or follow-up visit(s);
- Dihydrotestosterone at Week 5, Week 25, and Week 49 visits and/or follow-up visit(s);
- Sex hormone binding globulin at Week 5, Week 25, and Week 49 visits and/or follow-up visit(s).

9.7. Exploratory Analyses

Overall survival: Overall survival defined as time from randomization to date of death prior to data cutoff date. Kaplan-Meier methods will be used to describe survival distributions for each treatment arm.

Pharmacogenomic analyses may be conducted to examine the contribution of genetic variance on drug response, for example, its efficacy and safety, pending availability of samples.

Polymorphisms in germline genes related to the hypothalamic-pituitary-androgen pathway, prostate cancer risk, or to drug metabolizing enzymes and transporter proteins that might be implicated in the drug disposition, safety, or efficacy of relugolix. These analyses will be detailed in a separate statistical analysis plan and associated reports.

9.8. Interim Analyses

There will be no planned interim efficacy analysis for the study.

9.9. Sample Size

To calculate the sample size required for the primary efficacy endpoint of this study, the following assumptions have been made:

- True probabilities of sustained testosterone suppression are 94% and 96% for relugolix and leuprolide acetate, respectively;
- 2:1 randomization ratio (relugolix:leuprolide acetate); and
- Dropout rate of 15%.

The assumed probability of sustained testosterone suppression for relugolix arm is 94%. It was estimated based on the predicted dose-response relationship for the effect of relugolix on testosterone suppression in patients with prostate cancer (data from phase 2 studies C27002 and C27003). The assumed castration rate of 96% for leuprolide acetate was based on the results from degarelix phase 3 registration program [Shore, 2013].

For Evaluation Criterion 1, 610 patients in the relugolix group will provide approximately 90% power to rule out a fixed probability of sustained testosterone suppression of < 90% at a two-sided type I error rate of 0.05.

For Evaluation Criterion 2, with the non-inferiority margin of -10% and an overall 2-sided type I error rate of 0.05, a total of approximately 915 patients (610 relugolix, 305 leuprolide acetate) will yield at least 99% power in declaring the non-inferiority of relugolix compared to leuprolide acetate.

The primary analysis will be performed separately for individual evaluation criterion using data collected through 48 weeks after enrollment of approximately 915 patients.

Approximately 915 patients will be randomized in order to fulfill the regulatory requirements of all participating countries included in the primary efficacy endpoint of this study.

The study is also powered for the secondary endpoint of TCR in the high-risk subgroup of metastatic patients. Approximately 107 confirmed castration-resistance events (PSA progressions while castrated or deaths due to any cause) will need to be observed (or approximately 390 metastatic patients will need to be enrolled) to detect a hazard ratio of 0.55 (relugolix versus leuprolide acetate) with 85% power with a two-sided type I error of 5%, assuming a castration-resistant event-free rate of 60% at 48 weeks for the control arm, an 18-month enrollment period, 12 months of additional follow-up, and a 15% dropout rate.

With a total of approximately 1100 patients (metastatic or non-metastatic) randomized into the study including approximately 138 Chinese patients, it is anticipated to observe approximately 149 confirmed castration-resistant events (PSA progression while castrated or deaths due to any cause). Assuming an 18-month enrollment period, 12 months of additional follow-up, and a 10% dropout rate the study will provide approximately 85% power to detect a hazard ratio of 0.6 (relugolix versus leuprolide acetate) with a two-sided type I error of 5%.

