9.1. Randomization Methods

Central randomization will be used and treatment allocation will be 2:1, relugolix to leuprolide acetate 3-M depot. Randomization will be stratified by the following factors:

- Geographic Region: North and South America versus Europe versus Asia and Rest of World;
- Presence of Metastatic Disease (metastases in regional lymph node[s] are considered N1 and will, therefore, be stratified as non-metastatic): yes versus no;
- Baseline Age: ≤ 75 years old versus > 75 years old.

Stratified efficacy analyses will incorporate these 3 stratification factors unless otherwise specified.

After the first 915 patients are enrolled, enrollment in China will continue for metastatic and non-metastatic patients until the target number of Chinese patients is reached (138 patients). In the rest of the world, only metastatic patients will continue to be enrolled until approximately 390 metastatic patients are accrued.

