- Absolute values and changes from baseline of the remaining domains in the EORTC QLQ-C30 and EORTC QLQ-PR25, as well as EQ-5D-5L will be summarized by treatment group. The least square means at Week 49 will be compared between the relugolix group and the leuprolide acetate group by constructing a 95% confidence interval for the difference in the least square means using a mixed model for repeated measures;
- Time to PSA progression;
 - PSA progression is defined per Prostate Cancer Clinical Trials Working Group 3 guidelines [Scher, 2016] as the first increase in PSA of 25% or greater and 2 ng/mL or greater above the nadir with confirmation by a second PSA measurement at least 3 weeks later. For patients without declining PSA from baseline, PSA increase of 25% or greater and 2 ng/mL from baseline beyond 12 weeks will be considered PSA progression

- TCR in the subgroup of metastatic patients and the extended ITT population will only be evaluated at the time of final analysis, when approximately 390 metastatic patients have been randomized to the study and have had the opportunity to be evaluated for 48 weeks of study treatment and complete the 30-day safety follow-up visit or discontinued early. TCR will be evaluated first in the subgroup of metastatic patients at a two-sided significance level of 0.05. TCR in the extended ITT population will be tested only if the two-sided p-value in the subset of metastatic patients is < 0.05.
 - TCR is defined as the time from the date of first dose to the date of PSA progression while castrated or death due to any reason, whichever occurs earlier. TCR will be analyzed using the Kaplan-Meier method. Treatment comparison with hazard ratios will be performed using Cox proportional hazards model.

Additional details of the secondary analyses will be described in the statistical analysis plan.

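### The 85% power stated for TCR in all 1100 patients is the power of that test alone; behind the metastatic gate the chance of success is about 78–80%

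*Protocol*

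**What the plan says.** The amended protocol plans two TCR tests, and Section 9.9 sizes each one.

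- **Metastatic subgroup:** about 390 patients and 107 events, hazard ratio 0.55, 85% power, two-sided 5%, control event-free rate 60% at 48 weeks, with "12 months of additional follow-up, and a 15% dropout rate".
- **Extended ITT population:** "With a total of approximately 1100 patients (metastatic or non-metastatic) randomized into the study", where "it is anticipated to observe approximately 149 confirmed castration-resistant events". The paragraph ends: "and a 10% dropout rate the study will provide approximately 85% power to detect a hazard ratio of 0.6", again at two-sided 5%. The synopsis repeats this.

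Section 9.3.2 then orders the tests. The metastatic subgroup comes first at two-sided 0.05, and "TCR in the extended ITT population will be tested only if the two-sided p-value in the subset of metastatic patients is < 0.05". Section 9.1 sets the allocation at 2:1, relugolix to leuprolide.

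**The concern.** Under the rule in Section 9.3.2, a significant TCR result in the extended ITT population needs two successes: the metastatic test and then the extended ITT test. Section 9.9 states what the study will provide for the second test but gives a figure that holds only if the gate is ignored. It does not call that figure a marginal (ungated) power.

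The gate also sets a ceiling. The chance of passing both tests cannot exceed the power of the metastatic test, itself stated as 85%. An 85% chance in the extended ITT population would need every metastatic win to be followed by a win in the whole population.

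At stake is how a reader judges the chance of a TCR claim in the full population. Error control is not at stake, because the gate protects it.

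A smaller point is that the extended ITT calculation assumes 10% dropout while the metastatic TCR calculation assumes 15%, and no reason is given for the difference.

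**Working it through.** **Inputs, all from Sections 9.1, 9.3.2 and 9.9.** Extended ITT: 149 events, HR 0.6. Metastatic: 107 events, HR 0.55. Two-sided alpha 0.05, allocation 2:1, gate at metastatic p < 0.05.

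**Step 1: reproduce the plan's figures.** Schoenfeld: power = Φ(√(d × 2/3 × 1/3) × |ln HR| − 1.96).

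- Extended ITT: √(149 × 2/9) × 0.5108 = 5.754 × 0.5108 = 2.939; Φ(2.939 − 1.960) = 83.6%.
- Metastatic: √(107 × 2/9) × 0.5978 = 4.876 × 0.5978 = 2.915; Φ(2.915 − 1.960) = 83.0%.

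Other standard approximations with 2:1 allocation give 87–88% for each, so about 85% is a fair figure for each test taken alone. An exponential model with 60% of controls event-free at 48 weeks, 15% dropout and 48 weeks of follow-up gives 107.3 metastatic events, which matches the plan's 107.

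**Step 2: correlation.** The metastatic patients are part of the extended ITT population. If their 107 events are among the 149, the log-rank statistics correlate at about √(107/149) = 0.847.

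**Step 3: chance of passing both tests.** This is P(Z₁ > 1.96 and Z₂ > 1.96) for a bivariate normal pair with that correlation, recomputed where the event count changes. A Monte Carlo check of the first row gave 79.9%.

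| Scenario | Metastatic alone | Extended ITT alone | Both |
|---|---|---|---|
| Both powers as stated | 85% | 85% | 79.9% |
| Schoenfeld, plan's events and HRs | 83.0% | 83.6% | 77.8% |
| As stated, extended ITT scaled to 15% dropout (141 events) | 85% | 82.9% | 79.0% |
| Schoenfeld, 15% dropout, 141 events | 83.0% | 81.5% | 77.0% |
| Schoenfeld, 15% dropout, 145 events | 83.0% | 82.6% | 77.4% |
| Sensitivity: HR 0.6 in both populations | 70.2% | 83.6% | 68.3% |
| Sensitivity: HR 0.55 in both populations | 83.0% | 93.1% | 82.1% |

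The 141 events are 149 × 0.85/0.90. The 145 come from an exponential model whose control event-free rate (81%) was solved to give 149 events at 10% dropout; the protocol does not state that rate.

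**Step 4: what the plan's hazard ratios imply.** Weighting log hazard ratios by events, (ln 0.6 − 0.718 × ln 0.55)/0.282 = −0.289, so the non-metastatic HR is about 0.75. Log-rank simulation with 0.55 and 0.75, and an assumed 92.5% of non-metastatic controls event-free at 48 weeks, gives 78–79% for passing both tests, in line with the table.

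**Step 5: dropout.** Moving the extended ITT calculation from 10% to 15% costs 4 to 8 events, one to two points on the single test and about one point or less on the joint figure.

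**The case against.** The strongest reply is that 85% is not an error. It reproduces, and quoting the power of a later test in a hierarchy without its gate is common. That stands: the arithmetic is right. What remains is that this protocol fixes the gate itself, states what the study will provide, and does not say that the figure is ungated.

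It is also true that all secondary endpoints sit behind the primary endpoint and that Section 9.3.2 leaves the full multiplicity procedure to the SAP. The 78–80% therefore takes everything before the TCR tests as passed.

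Four stronger readings are tempting, and the documents do not support them.

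- **A joint chance near 72% or lower.** Multiplying 0.85 × 0.85 = 72% treats the tests as independent, although most events are shared. Values of about 70% (68% by formula, 72–73% by simulation) also arise if the metastatic HR is 0.6. The plan assumes 0.55 there, and in simulation HR 0.6 throughout produces 112–115 metastatic events, not 107.
- **Dropout rates that cannot all hold.** 15% of 915 is 137, more than 10% of 1100 (110), but this sets a rate for the testosterone endpoint against one for TCR. Within TCR the rates can coexist: 15% of 390 is 58.5, leaving 51.5 of 710 (7.3%) for the rest. The 10% is unexplained rather than impossible.
- **A test fixed as unstratified.** Section 9.3.2 says "Treatment comparison with hazard ratios will be performed using Cox proportional hazards model" and is silent on strata. Section 9.1 says "Stratified efficacy analyses will incorporate these 3 stratification factors unless otherwise specified", and details are left to the SAP. Stratifying by metastatic status gained a few points in simulation, but nothing here shows that it will be left out.
- **Extra enrolment that rests on this figure.** The synopsis and Section 4.2 base it on about 390 metastatic patients for TCR and on 138 Chinese patients for registration.

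**Conclusion.** The point holds as a matter of what the 85% means. It is the power of the extended ITT test before the gate. With the gate in Section 9.3.2, the chance of a significant extended ITT result is about 78–80% at the plan's own effects, five to seven points lower; using 15% dropout throughout makes it about 77–79%.

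This rests on proportional hazards, joint normality of the two statistics, a correlation set by the shared event fraction, and the 107 metastatic events being among the 149. The result depends most on the metastatic hazard ratio: about 70% if it were 0.6, which the plan does not assume, and about 82% if the hazard ratio were 0.55 in both populations. The dropout discrepancy is real but small. Neither the type I error nor the metastatic power statement is affected.

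**What to change.** In Section 9.9 and the synopsis:

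1. Say that about 85% is the power of the extended ITT TCR test taken alone, before the metastatic gate.
2. Add the gated power of about 78–80%, with its assumptions: HR 0.55 metastatic and 0.6 overall, 107 of 149 events shared, and the earlier steps of the hierarchy passed.
3. Reconcile the 10% dropout rate with the 15% in the metastatic TCR calculation, or give the reason for the difference. If 15% is adopted, update the event count and both powers.

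Optionally, confirm in Section 9.3.2 or the SAP that the extended ITT TCR analysis is stratified by the randomisation factors, as Section 9.1 suggests.

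The cost is a few sentences and a slightly less favourable stated power. No extra patients, no change to the testing order and no change to the significance levels are needed.

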10. RESPONSIBILITIES

10.1. Investigator Responsibilities

10.1.1. Good Clinical Practice

The investigator will ensure that this study is conducted in accordance with the principles of the “Declaration of Helsinki” (as amended in Edinburgh, Tokyo, Venice, Hong Kong, and South Africa), International Council on Harmonisation (ICH) guidelines, or with the laws and regulations of the country in which the research is conducted, whichever affords the greater protection to the study participant. For studies conducted under a US investigational new drug application, the investigator will ensure that the basic principles of “Good Clinical Practice,” as outlined in 21 Code of Federal Regulations (CFR) Part 312, subpart D, “Responsibilities of sponsors and investigators,” 21 CFR Part 50, and 21 CFR Part 56, are adhered to. These standards are consistent with the requirements of the European Community Directive 2001/20/EC.

Since this is a “covered” clinical study, the investigator will ensure that 21 CFR Part 54, is adhered to; a “covered” clinical study is any “study of a drug or device in humans submitted in a

marketing application or reclassification petition subject to this part that the applicant or FDA relies on to establish that the product is effective (including studies that show equivalence to an effective product) or that make a significant contribution to the demonstration of safety.” This requires that investigators and all sub-investigators must provide documentation of their financial interest or arrangements with the sponsor, or proprietary interests in the drug being studied. This documentation must be provided before participation of the investigator and any sub-investigator. The investigator and sub-investigator agree to notify the sponsor of any change in reportable interests during the study and for one year following completion of the study.

10.1.2. Institutional Review Board/Independent Ethics Committee Approval

This protocol and any accompanying material to be provided to the patient (such as advertisements, patient information sheets, or descriptions of the study used to obtain informed consent) will be submitted by the investigator to an IRB or IEC. Approval from the IRB or IEC must be obtained before starting the study and should be documented in a letter to the investigator specifying the protocol number, protocol version, protocol date, documents reviewed, and date on which the committee met and granted the approval.

Any modifications made to the protocol after receipt of IRB or IEC approval must also be submitted to the IRB or IEC for approval before implementation.

10.1.3. Informed Consent

A properly executed, written informed consent, in compliance with the Declaration of Helsinki, ICH Good Clinical Practice, US CFR for Protection of Human Subjects (21 CFR 50.25[a,b], CFR 50.27), and local regulations, will be obtained from each patient before entering the patient in the trial. The investigator is responsible for obtaining written informed consent from each individual participating in this study after adequate explanation of the aims, methods, objectives, and potential hazards of the study and before undertaking any study-related procedures. The investigator must utilize an IRB- or IEC-approved informed consent form for documenting written informed consent that contains all elements required by national, state, local, and institutional regulations or requirements. Each informed consent form will be appropriately signed and dated by the patient or the patient’s legally authorized representative and the person obtaining consent.

The investigator will provide copies of the signed informed consent form to each patient (or to the patient’s legal representatives) and will maintain the signed original document within the patient’s record file per local requirements. The investigator will also fully document the informed consent process in the patient’s source records.

10.1.4. Confidentiality

The investigator must assure that patients’ anonymity will be strictly maintained and that their identities are protected from unauthorized parties. Only patient number, date of birth, and an identification code (ie, not names) should be recorded on any form or biological sample submitted to the sponsor, IRB or IEC, or laboratory. The investigator must keep a screening log

showing codes, names, and addresses for all patients screened and for all patients enrolled in the study.

The investigator agrees that all information received from the sponsor, including but not limited to the Investigator Brochure, protocol, eCRFs and other study forms, the investigational drug, and any other study information, remain the sole and exclusive property of the sponsor during the conduct of the study and thereafter. This information is not to be disclosed to any third party (except employees or agents directly involved in the conduct of the study or as required by law) without prior written consent from the sponsor. The investigator further agrees to take all reasonable precautions to prevent the disclosure by any employee or agent of the study site to any third party or otherwise into the public domain.

The investigator must maintain adequate and accurate records to enable the conduct of the study to be fully documented and the study data to be subsequently verified. These documents should be classified into at least the following 2 categories:

- 1) Investigator's study file: The investigator's study file will contain the Investigator Brochure, protocol/amendments, IRB or IEC and governmental approval with correspondence, informed consent forms, drug records, staff curriculum vitae, authorization and training forms, and other appropriate documents and correspondence.
- 2) Patient clinical source documents: The required source data should include the following for each patient:
 - Patient identification (name, date of birth, gender);
 - Documentation that the patient meets eligibility criteria, (eg, history, physical examination, and confirmation of diagnosis to support inclusion and exclusion criteria);
 - Participation in the study (including study number);
 - Study discussed and date of informed consent;
 - Dates of all visits;
 - Documentation that protocol-specific procedures were performed;
 - Results of efficacy parameters, as required by the protocol;
 - Start and end date (including dose regimen) of study medication (drug dispensing and return should be documented as well);
 - Record of all adverse events and other safety parameters (start and end date, and causality and intensity as assigned by the investigator);
 - Concomitant medication (including start and end date); and
 - Date of study completion and reason for early discontinuation, if applicable.

All clinical study documentation must be retained by the investigator until at least 2 years after the last approval of a marketing application in an ICH region (ie, US, Europe, or Japan) and until there are no pending or contemplated marketing applications in an ICH region; or, if no application is filed or if the application is not approved for such indication, until 2 years after the investigation is discontinued and regulatory authorities have been notified. Investigators may be required to retain documents longer if required by applicable regulatory requirements, by local regulations, or by an agreement with the sponsor. The investigator must notify the sponsor before destroying any clinical study records.

Clinical study documentation includes the Investigator Brochure, signed protocol and amendments, signed informed consents, notification of serious adverse events and related reports, any dispensing and accountability logs, shipping records of investigational product and

study-related materials, documentation of financial aspects of the study, insurance statement, and signed agreement between the involved parties, dated and documented IRB/IEC approval, approval of regulatory authorities as applicable, curriculum vitae and all training records of study site personnel, and all correspondence pertaining to the conduct of the study.

Should the investigator wish to assign the study records to another party or move them to another location, the sponsor must be notified in advance.

If the investigator cannot guarantee this archiving requirement at the study site for any or all of the documents, special arrangements must be made between the investigator and the sponsor to store these in sealed containers outside of the site so that they can be returned sealed to the investigator in case of a regulatory audit. When source documents are required for the continued care of the patient, appropriate copies should be made for storage outside of the site.

